5.2. Handling of missing data and drop-outs

CARDIOBASE has very few missing cases for MACE, therefore, for MACE, a complete case analysis will be done. Activity data will be used when at least 7 days of 12 h/day (during day time) recording are available. Otherwise, these patients will be allocated to a non-compliant group for which patient characteristics will be summarised and compared to the compliant group. Patients of the non-compliant group will not be used for the analysis of the primary endpoint. For secondary outcomes, missing data will be imputed by multiple imputation.

In case of a large number of non-compliant patients (>50), additional patients will be recruited (if necessary recruitment period will be extended).

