Study procedures	Patients will receive the wrist band, the patient information sheet including informed consent (IC), the international physical activity questionnaire - short form (IPAQ-SF), and an addressed and prepaid envelope before hospital discharge. They are asked to read the patient information when arrived at home, sign the IC when willing to participate and wear the wrist band for two weeks. After that, they should complete the IPAQ-SF, send the wrist band and signed IC to our institute. Patients who do not want to participate in the study are asked to send back the activity tracker to our institution without signing the IC. Health related data and information regarding CR uptake will be derived from the clinic's patient information system for all patients who have either signed the study IC or have not withdrawn the clinics' general informed consent to further use of data for research. MACE, patient characteristics, patient history, risk factors and comorbidities will be extracted from CARDIOBASE Bern PCI registry (ClinicalTrials.gov Identifier: NCT02241291). Patients attending the clinical routine check-up after 12 months in our institution will be asked to wear the activity tracker again for two weeks.
Study Duration and Schedule	Recruitment will last for 16 months. 10/2020 First-Participant-In 04/2023 Last-Participant-Out
Investigator(s)	[name]. med. [name] Leitender Arzt und Zentrumsleiter Präventive Kardiologie & Sportmedizin Universitätsklinik für Kardiologie, Inselspital, [name] [contact] [contact] PD Dr. [name] Forschungsleiterin Präventive Kardiologie & Sportmedizin Universitätsklinik für Kardiologie, Inselspital, [name] [contact] [contact]
Study Center(s)	Präventive Kardiologie & Sportmedizin Universitätsklinik für Kardiologie, Inselspital, [name]
Data privacy	Patients will be coded and code key will be stored in secure place.
Ethical consideration	Many studies have found a strong association between physical activity and survival. Some recent studies with patients after major surgery have found daily steps/physical activity level to be a strong predictor for MACE after hospital discharge. If this can be confirmed in patients after PCI, then step monitoring will be an easy, cheap and unintrusive routine clinical assessment to identify patients at high risk for MACE, who consequently can be followed up more closely.

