3 STUDY OBJECTIVES AND DESIGN

3.1 Primary objective and hypothesis

Quantification of physical activity (daily steps) during the first two weeks after hospital discharge as a predictor for MACE at one year.

Hypothesis I: Daily steps measured during the first two weeks after hospital discharge from PCI is a significant independent predictor additional to traditional risk factors for MACE at one year after PCI.

Secondary objectives and hypothesis

1. Comparison between daily steps and objectively measured activity counts (divided in time spent in moderate-to-vigorous activity, light activity and sedentary activity), as well as patient reported activity:

Hypothesis I: Objectively monitored activity counts two weeks after hospital discharge is significantly associated with daily step counts and self-reported activity level

Hypothesis II: Predictive value of daily step count during the first two weeks after hospital discharge is significantly better than the predictive value by patient reported physical activity for MACE at 12 months.

2. Association of daily steps after one year with reaching targets for systolic blood pressure, low-density lipoprotein cholesterol (LDL-C), body mass index (BMI) and glycated haemoglobin (HbA1c):

Hypothesis I: Patients with higher daily step counts during the first two weeks after hospital discharge have higher achievement rates of target levels at 12 months for blood pressure, body weight, blood lipids, and blood sugar.

3. Comparison of daily steps after hospital discharge and MACE between non cardiac rehabilitation (CR), conventional hospital based CR, tele-CR and modular CR participants.

Hypothesis I: Tele-rehabilitation and conventional CR patients achieve higher daily step counts (corrected for age, risk factors and comorbidities) at two weeks after PCI than patients who decline any form of CR.

Hypothesis II: Tele-rehabilitation and conventional CR patients a lower risk of MACE within one year than patients who decline any form of CR

4. Comparison of daily steps at one year after hospital discharge in different CR groups.

Hypothesis I: Tele-rehabilitation is not inferior to conventional ambulatory cardiac rehabilitation (CR) in increasing daily steps from two weeks after PCI to 12 months after PCI

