3.2 Primary and secondary endpoints

Primary endpoint: Occurrence of MACE within 12 months after PCI

Secondary endpoints: BMI, systolic BP, LDL-C, HbA1c and daily steps two weeks and 12 months after PCI; proportion and patient characteristics of CR participants and non-participants

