5 STATISTICS AND METHODOLOGY

5.1. Statistical analysis plan and sample size calculation

Predictive value of daily steps during the first two weeks after hospital discharge is quantified by net reclassification improvement (NRI) and by increase of area under the curve (AUC) of the receiver operating characteristic curve (ROC) of a model consisting of traditional risk factors (age, sex, cardiovascular risk factors, cardiovascular history, comorbidities).

Descriptive statistics are used to quantify and characterise the populations who choose conventional hospital based CR, tele-rehabilitation, and modular CR in terms of number, age, sex, medical history, cardiovascular risk factors and comorbidities. MACE at one year follow-up and daily steps during the first two weeks after hospital discharge will be compared between the CR and non CR participants using multivariate modelling adjusted for potential confounding factors. Further, for patients who perform their yearly routine follow-up visit at our centre, data on body mass index (BMI), systolic blood pressure (BP), low-density lipoprotein cholesterol (LDL-C) and smoking cessation will be derived from the clinic's patient information system and compared between different forms of CR. Also, daily steps after 12 months from patients who volunteer to monitor steps again will be quantified for the different CR groups and tested between the groups if sufficient data can be gathered. The same will be done for changes in daily steps between the first two weeks after hospital discharge and at 12 months.

Sample Size:

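### The tracker-compliance exclusion in section 5.2 is tied to MACE rather than to step-count analyses, so read literally it also removes patients from the CR versus no-CR comparison of MACE

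*SAP*

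**What the plan says.** Section 5.2 sets the validity rule for tracker data: "Activity data will be used when at least 7 days of 12 h/day (during day time) recording are available". Patients who fall short form a non-compliant group, which is described and compared with the compliant group. The rule for this group is "Patients of the non-compliant group will not be used for the analysis of the primary endpoint". The same section plans a complete-case analysis for MACE and multiple imputation for secondary outcomes.

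Section 3.2 defines the endpoint that the rule names: "Primary endpoint: Occurrence of MACE within 12 months after PCI". MACE is not among the secondary endpoints listed there or in the synopsis.

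The CR comparison uses the same endpoint. Section 3.1, secondary objective 3, Hypothesis II reads: "Tele-rehabilitation and conventional CR patients a lower risk of MACE within one year than patients who decline any form of CR". Section 5.1 gives the analysis: "MACE at one year follow-up and daily steps during the first two weeks after hospital discharge will be compared between the CR and non CR". This comparison is adjusted for confounders, and no analysis set is named for it.

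On data sources, the synopsis (Study procedures) says that health data and CR uptake come from clinic records, and gives the group covered as "for all patients who have either signed the study IC or have not withdrawn". What must not have been withdrawn is the hospital's general consent to research use. On the remaining variables the synopsis adds: "MACE, patient characteristics, patient history, risk factors and comorbidities will be extracted from CARDIOBASE Bern PCI registry". Section 4.4 makes MACE data subject to the registry's own consent.

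**The concern.** The exclusion is attached to an endpoint, not to a particular analysis. It is natural in the primary prediction model, because a patient without valid step data has no exposure value. In the CR comparison of MACE, the exposure is CR status, the outcome is MACE and the adjustment variables come from the registry. None of these needs a tracker. The sentence on secondary outcomes does not provide an exception, because MACE is not listed as a secondary endpoint.

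Two things are at stake.

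- **Selection.** Whether a patient records 7 valid days is known only after discharge. A patient who is readmitted or dies early may be unable to reach 7 days, so exclusion can depend on the outcome. Compliance may also follow motivation, which may relate to both CR uptake and risk. Adjustment for the planned confounders need not remove this.
- **An open choice.** Two analysts could each defend a different analysis set for Hypothesis II, and nothing fixes the choice before the data are seen.

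**Working it through.** **1. The plan's own figures.** Inputs from section 5.1: HR 2.66, alpha 0.05 (taken as two-sided), power 80%, two quartiles of equal size.

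Schoenfeld: D = (1.960 + 0.842)² / (0.25 × (ln 2.66)²) = 7.849 / (0.25 × 0.957) = 32.8, so 33 events. Doubled for the whole sample this is 66. Then 66 / 0.08 = 825 patients, and 825 / 600 × 12 = 16.5 months. The stated 33, 66, 825 and roughly 16 months all reproduce and are not in dispute. They concern steps and MACE; the plan gives no sample size for the CR comparison.

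**2. Direct loss from the exclusion.** Events lost = number non-compliant × 8%, if risk is equal in both groups.

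| Non-compliant of 825 | Events lost | Events left |
|---|---|---|
| 50 (the trigger in section 5.2) | 4.0 | 62.0 |
| 10% (assumed), 82.5 | 6.6 | 59.4 |
| 20% (assumed), 165 | 13.2 | 52.8 |

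Above 50 non-compliant patients, section 5.2 provides for further recruitment. This may restore the event count, but it does not bring back the excluded patients, so the selection remains.

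If non-compliant patients carry twice the risk (assumed) while the overall rate stays 8%, the rate in compliant patients is 0.08 / (1 + f), where f is the non-compliant fraction. With f = 50/825 = 0.061 this is 0.0754, and the loss is 50 × 2 × 0.0754 = 7.5 events. At 10% and 20% non-compliance the loss is 12 and 22.

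**3. Effect on precision.** SE(log HR) = 1 / √(D × a × (1 − a)), where a is the share in CR. The documents do not give a; 0.5 is assumed here.

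- D = 66: 1 / √16.5 = 0.246
- D = 62: 1 / √15.5 = 0.254

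The increase is √(66/62) − 1 = 3%, whatever the split.

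**4. Ceiling if tracker decliners are added.** Section 5.1 counts about 1200 potential patients per year. 1200 × 16/12 = 1600 patients, and 1600 × 0.08 = 128 MACE. The 1200 is counted by age under 80 only. It is not reduced for the eligibility criteria in section 4.1 or for the general and registry consents, so 128 is an upper bound.

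Power = Φ(|ln HR| × √(D × a × (1 − a)) − 1.96), at an assumed HR of 0.6:

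| Events | a = 0.5 | a = 0.3 |
|---|---|---|
| 62 | 52% | 45% |
| 66 | 55% | 48% |
| 128 (upper bound) | 82% | 75% |

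The step from 62 to 66 comes from narrowing the exclusion. The step from 66 towards 128 comes only from adding patients who never joined the tracker study.

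**The case against.** The exclusion sentence speaks of a single analysis and closely follows the rule for usable activity data. The authors may well have meant only the model of steps predicting MACE. Section 5.1 puts no tracker condition on the CR comparison, and the synopsis plans to collect CR uptake beyond those who sign the study consent, which suggests that a wider set was in mind. This is a fair reading and may be the intended one, but the text neither says so nor names a set for Hypothesis II.

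A reader might infer that the exclusion throws away about half the available events. It does not. The non-compliant group consists of participants with too little recording; people who decline the tracker were never in it. Rewording section 5.2 alone recovers about 4 events at the 50-patient trigger.

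A reader might also infer that the bias runs towards no difference. The documents do not settle this. Restricting to motivated wearers could instead reduce confounding by motivation, and adding decliners could increase it and exaggerate an apparent benefit of CR. The wider set is larger, but not clearly less biased in every respect.

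Two further points stand. The synopsis sentence on MACE does not say that decliners are covered, so including them depends on consent. And this is one secondary hypothesis in a study that calls itself explorative, with no power claimed for it.

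**Conclusion.** The point holds as a defect of scope. The exclusion in section 5.2 is unrestricted, and taken literally it drops patients with usable CR and MACE data from Hypothesis II on a criterion that plays no part in that comparison. The plan does not expressly confine the comparison to compliant wearers; it leaves the matter open.

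The direct cost is small: about 4 of 66 events and a 3% wider standard error at 50 non-compliant patients, or about 7 to 13 events at an assumed 10 to 20%, before any replacement recruitment. These figures rest on the plan's 8% rate and on equal risk in both groups. The more important matter is selection on a post-discharge criterion that early events can affect, with unknown direction. The gain from adding decliners is separate, capped at about 128 events, and smaller by an amount the documents do not allow one to estimate. The primary step-count analysis is unaffected. This is a cheap improvement to a secondary analysis.

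**What to change.** - **Section 5.2:** state that non-compliant patients are left out only of analyses in which daily steps or activity is the predictor or the outcome.
- **Section 5.1:** name the analysis set for Hypothesis II of secondary objective 3 as all enrolled patients with usable registry MACE data, whatever their tracker compliance. Extend it to eligible patients who declined the tracker where both the general consent and the registry consent permit.
- **Sensitivity analysis:** repeat the comparison in the tracker-compliant subset. Reporting results with and without decliners as well would show how far the answer depends on motivation.

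For enrolled patients the cost is wording only, since the data sources are already planned. Adding decliners needs a larger merge of clinic and registry data, confirmation that the consents cover it, and a check against the amendment rules in section 6.6, because it widens the analysed population. It may also bring extra confounding by motivation, which the sensitivity analysis would help to show.

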Endpoint(s)	Primary endpoint: MACE at one year after PCI. Secondary endpoints: BMI, systolic BP, LDL-C, HbA1c 12 months after PCI; daily steps and activity level two weeks and 12 months after PCI hospital discharge; proportion and patient characteristics of CR participants and non-participants
Study Design	Observational single centre study.
Statistical Considerations	Predictive value of daily steps during the first two weeks after hospital discharge is quantified by net reclassification improvement (NRI) and by increase of area under the curve (AUC) of the receiver operating characteristic curve (ROC) of a model consisting of traditional risk factors (age, sex, cardiovascular risk factors, cardiovascular history, comorbidities).
Inclusion- / Exclusion Criteria	Inclusion criteria: Patients after PCI younger than 80 years of age who are eligible for ambulatory CR. Exclusion criteria are inability to participate in ambulatory CR (nursing home residence, stationary CR, orthopedic or neurologic impairment prohibiting physical exercise, psychiatric conditions), and staged PCI.
Number of Participants with Rationale	The sample size is based on a previous study who found a significant difference between the quartile with lowest versus highest self-reported physical activity on MACE at 3 years after PCI. Based on this, we would need 33 events to reach a significance level of 0.05 and a power of 80% in these two quartiles or 66 events in the whole sample. According to data from CARDIOBASE Bern PCI registry, we can expect 100 MACE per year in approximately 1200 patients younger than 80 years of age undergoing PCI at our centre. If we assume that

	50% of these patients are willing to participate in our study, we could recruit about 800 patients in 16 months, who will have approximately 66 MACE within one year.
Study Intervention	Patients will be provided with an activity tracker in the form of a wrist band that they should wear continuously for two weeks after hospital discharge. After 12 months, they will be asked to wear the activity tracker again for two weeks in case they attend the clinical routine check-up in our institution.
Control Intervention	None

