Based on a study on nearly 9000 PCI patients, physical activity level assessed by the Duke Activity Status Index (DASI) questionnaire found a 4.8-fold increase in future risk of incident major adverse cardiac events at 3 years in the quartile with lowest DASI compared to the highest quartile.(6) The DASI score reclassified 15% of patients ($P<0.001$) beyond traditional risk factors in predicting future MACE.(6) In the approximately 6500 patients with obstructive CAD, the adjusted HR (adjusted for traditional risk factors and history of heart failure and peripheral arterial disease) for MACE in the lowest DASI quartile compared to the highest quartile was 2.66 (95% CI 2.16 to 3.27). According to this relative hazard, 33 events would be needed to reach a significance level of 0.05 and a power of 80% in these two quartiles. For the whole sample this would be 66 events. According to data from CARDIOBASE, in the 10 years from 2009-2018 1083 (8%) of patients younger than 80 years had a MACE between 7 and 365 days after PCI, which corresponds to approximately 100 MACE per year. During the last 3 years (Oct 2015 to Oct 2018), 3683 patients younger than 80 years were recruited for CARDIOBASE, which equates to approximately 1200 potential study patients per year. If we assume that 50% of these patients are willing to participate in our study (wear an accelerometer for 2 weeks after discharge), we could recruit about 600 patients per year, of whom approximately 48 (8%) will have a MACE within 12 months following PCI. To reach 66 MACE we will need to recruit 825 patients which will require

a recruitment period of approximately 16 months.

Statistical analyses will be performed by [name] (CAS in statistics of the University of Bern) using the software R.

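### The 825 recruits in section 5.1 include no allowance for the tracker exclusions in section 5.2, so 66 events and 80% power are expected only if no recruit is excluded

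*SAP*

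**What the plan says.** SAP section 5.1 takes a hazard ratio of 2.66 between the lowest and highest activity quartiles and concludes that "33 events would be needed to reach a significance level of 0.05 and a power of 80% in these two quartiles". It doubles this to 66 events for the whole sample and, at an 8% one-year MACE rate, states: "To reach 66 MACE we will need to recruit 825 patients". The recruitment rate behind the 16-month period comes from a participation assumption: "If we assume that 50% of these patients are willing to participate in our study (wear an accelerometer for 2 weeks after discharge".

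Section 5.2 sets the validity rule for tracker data: "Activity data will be used when at least 7 days of 12 h/day (during day time) recording are available". For those who fall short, "Patients of the non-compliant group will not be used for the analysis of the primary endpoint". The remedy is conditional: "In case of a large number of non-compliant patients (>50), additional patients will be recruited", with the note "if necessary recruitment period will be extended". No number to add and no stopping point is given.

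The synopsis (section 1) and section 4.1 speak of about 800 patients. The synopsis bases this on a slightly different rate: "we can expect 100 MACE per year in approximately 1200 patients younger than 80 years of age undergoing PCI at our centre".

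**The concern.** Section 5.1 counts patients recruited, while the primary analysis under section 5.2 counts patients with valid step data. The figure of 825 serves as both. It is the exact quotient of the event target and the event rate, so each exclusion that is not replaced is expected to take the yield below 66 events. Section 5.2 foresees such exclusions, requires no action for up to 50 of them, and above 50 leaves the size of the top-up open.

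At stake is whether the stated event count and power are what the two sections together secure, and whether the team will know when added recruitment may stop.

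**Working it through.** **Inputs.** From section 5.1: hazard ratio 2.66, significance level 0.05, power 80%, MACE rate 8%, 600 recruits per year (50 per month). From section 5.2: exclusion of non-compliant patients, and a trigger at more than 50. Sidedness is not stated. Two-sided is inferred because it reproduces the plan's 33 events with the Schoenfeld formula; one-sided gives 26.

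**Step 1: reproduce the plan.**
- Events in two equal groups: 4 × (1.960 + 0.842)² / (ln 2.66)² = 32.8, rounded up to 33.
- Whole sample, on the plan's premise that half of all events fall in the two extreme quartiles: 2 × 33 = 66.
- Patients: 66 / 0.08 = 825 exactly.
- Duration: 825 / 50 = 16.5 months, in line with the stated period of about 16 months.

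Every printed figure reproduces, and none contains a term for loss after recruitment.

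**Step 2: apply section 5.2.** Let x be the number of exclusions not replaced, and assume that excluded patients have the same 8% MACE rate.
- Expected events: E = (825 − x) × 0.08.
- Events in the two quartiles: d = E / 2.
- Power = Φ(√(d/4) × ln 2.66 − 1.960), with ln 2.66 = 0.978.

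| Unreplaced exclusions | Analysable | Events | In two quartiles | Power |
|---|---|---|---|---|
| 0 | 825 | 66 | 33 | 80.2% |
| 25 | 800 | 64 | 32 | 79.0% |
| 50 | 775 | 62 | 31 | 77.7% |

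At the threshold the shortfall is 4 events and 80.2 − 77.7 = 2.5 percentage points.

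**Step 3: above the threshold.** Section 5.2 requires more patients but gives no number. Replacing only the excess over 50 would satisfy the text and return the analysable number to 775, hence 62 events. Adding fewer would also satisfy it, so as written the rule fixes no minimum.

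**Step 4: cost of full replacement.** The documents give no non-compliance rate. Taking the trigger share as an assumption, 50 / 825 = 6.1%, recruitment for 825 analysable patients is 825 / (1 − 50/825) = 878.2, rounded up to 879. That is 54 more, and 54 / 50 is about 1.1 months.

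**Step 5: 800 against 825.** The synopsis rate is 100 / 1200 = 8.33%, and 800 × 0.0833 = 66.7 events, so about 800 agrees with its own rate. At that rate the exact target would be 66 / 0.0833 = 792. The difference is one of rounding between sections.

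**The case against.** **The plan already deals with the loss.** Section 5.2 names non-compliance, sets a threshold and allows recruitment to be extended. Tolerating up to 50 exclusions, 6.1% of 825, may be deliberate. This largely stands: the tolerance is a legitimate choice. What remains is that section 5.1 does not show its consequence and section 5.2 does not say where a triggered top-up ends.

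**The willing 50% already excludes non-wearers.** Section 5.1 describes the willing as those who wear the device for two weeks. Under sections 3.4 and 4.2, signed consent comes back with the tracker after the wearing period, and the unwilling can return the device straight away. Many non-wearers may therefore never count as recruited, which makes 50 exclusions less likely. But the 50% is used only to get from 1200 to 600 patients a year, and section 5.2 provides for a non-compliant group all the same. Partial wear below the 7-day rule is not covered.

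**The effect is smaller than the uncertainty in the inputs.** This is true. With 10 exclusions the power is 79.8%. The confidence limits that section 5.1 quotes for the hazard ratio, 2.16 and 3.27, move the power at 66 events from about 60% to about 93%. This is why the point is minor.

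**Stronger readings that the documents do not support.** A reader might infer that the study expects 78% power; but 50 is a trigger and no non-compliance rate is given. A reader might infer that the primary analysis is underpowered; but section 5.1 calculates power for a two-quartile hazard comparison, whereas the predictive value is to be quantified by NRI and AUC increase, for which no power is stated. A reader might also infer an arithmetic slip in section 5.1; there is none.

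**Conclusion.** The point holds and is minor. The stated 66 events and 80% power are the expected result of recruiting 825 only if none of them is excluded under section 5.2. With 0 to 50 exclusions, the range in which the rule requires no action, the expected yield is 66 down to 62 events and the power 80.2% down to 77.7%. Above 50, the yield depends on a number the plan does not give.

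This rests on the two-sided Schoenfeld formula, on the plan's premise that half of all events fall in the extreme quartiles, and on excluded patients sharing the 8% MACE rate. If their rate were higher, more events would be lost; if lower, fewer. The documents give no figure for this.

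**What to change.** Choose one.

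**(a) Keep the threshold and state what it delivers.** In section 5.1, say that 825 is the number recruited and that with up to 50 exclusions the expected yield is 62 to 66 events, with about 78% to 80% power for the two-quartile comparison. In section 5.2, say that once the trigger is met, recruitment continues until at least 775 patients are analysable, which is the minimum the rule already tolerates (825 − 50). Cost: wording only, with no added patients unless the existing trigger is met.

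**(b) Make 825 the analysable target.** Define 825 in section 5.1 as patients with valid step data by the section 5.2 rule. Drop the threshold, so that every non-compliant patient is replaced through the extension section 5.2 already allows. Cost: it depends on the non-compliance rate; at an assumed 6.1%, 879 recruited, 54 more than 825, about one month at 50 per month.

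Under either choice, use one MACE rate and one patient number in sections 1, 4.1 and 5.1. The figures above are at 8%. If the synopsis rate of 8.33% is preferred, 792 takes the place of 825, and the minimum under (a) becomes 792 − 50 = 742.
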